6.6.2 Lenvatinib

Lenvatinib dose reduction and interruption for participants who experience lenvatinib-related or lenvatinib-pembrolizumab combination therapy-related toxicity will be in accordance with the dose modification guidelines described in [Table 6](#). An interruption of study intervention for more than 28 days will require Sponsor approval before treatment can be resumed.

Adverse events will be graded using NCI CTCAE v4.0. Investigators will decide the probability of the event being related to one or both drugs as to whether dose modification of one or both drugs is required.

The starting dose of lenvatinib is 20 mg/day. Dose reductions of lenvatinib occur in succession based on the previous dose level (14, 10, and 8 mg/day). Any dose reduction below 8 mg/day must be discussed with the Sponsor. Once the study intervention dose has been reduced, it may not be increased at a later date unless the dose has been mistakenly decreased; in this situation, the Sponsor's approval is required to increase the dose.

Refer to the subsections below for management of hypertension (Section 6.6.2.1), proteinuria (Section 6.6.2.2), diarrhea (Section 6.6.2.3), hepatotoxicity (Section 6.6.2.4), thromboembolic events (Section 6.6.2.5), posterior reversible encephalopathy syndrome/ reversible posterior leukoencephalopathy syndrome (PRES/RPLS; Section 6.6.2.6), hypocalcemia (Section 6.6.2.7), hemorrhage (Section 6.6.2.8), gastrointestinal perforation or fistula formation (Section 6.6.2.9), and osteonecrosis of the jaw (Section 6.6.2.10) as appropriate, before consulting the dose modification table ([Table 6](#)). For overlapping toxicities of pembrolizumab and lenvatinib, please refer to Section 6.6.3.

Table 6 Dose Modification Guidelines for Lenvatinib-related Adverse Events

Treatment-Related Toxicity ^{a,b}	Management	Dose Adjustment
Grade 1 or Tolerable Grade 2		
	Continue treatment	No change
Intolerable Grade 2^{c,d} or Grade 3^{e,g}		
First occurrence	Interrupt lenvatinib until resolved to Grade 0-1, or tolerable Grade 2	Reduce lenvatinib dose to 14 mg once a day (1-level reduction)
Second occurrence (same toxicity or new toxicity)	Interrupt lenvatinib until resolved to Grade 0-1, or tolerable Grade 2	Reduce lenvatinib dose to 10 mg once a day (1-level reduction)
Third occurrence (same toxicity or new toxicity)	Interrupt lenvatinib until resolved to Grade 0-1, or tolerable Grade 2	Reduce lenvatinib dose to 8 mg orally once a day (1-level reduction)
Fourth occurrence (same toxicity or new toxicity)	Interrupt lenvatinib	Discuss with Sponsor
Grade 4^{f,g}: Discontinue Study Intervention		

Abbreviations: AE = adverse event; BMI = body mass index; CTCAE = Common Terminology Criteria for Adverse Events. Note: For grading see CTCAE version 4.0. Collect all AE grades (ie, decreasing and increasing CTCAE grade).

- a An interruption of study intervention for more than 28 days will require Sponsor’s approval before treatment can be resumed.
- b Initiate optimal medical management for nausea, vomiting, hypertension, hypothyroidism, and/or diarrhea prior to any lenvatinib interruption or dose reduction.
- c Applicable only to Grade 2 toxicities judged by the participant and/or physician to be intolerable.
- d Obese participants (BMI ≥ 30) with weight loss do not need to return to their baseline weight or within 10% of their baseline weight (ie, Grade 1 weight loss). These participants may restart study intervention at a lower dose once their weight remains stable for at least 1 week and they reach at least a BMI of 25. The new stable weight should be used as the new baseline for further dose reductions.
- e For asymptomatic laboratory abnormalities, such as Grade ≥ 3 elevations of amylase and lipase that are not considered clinically relevant by the investigator, continuation of treatment should be discussed with Sponsor.
- f Excluding laboratory abnormalities judged to be nonlife-threatening, in which case manage as Grade 3.
- g For Grade 3 thromboembolic event, permanently discontinue lenvatinib. See Section 6.6.2.5.

6.6.2.1 Management of Hypertension

Hypertension is a recognized side effect of treatment with drugs inhibiting VEGF signaling. Investigators should therefore ensure that participants enrolled to receive treatment with lenvatinib have BP of $\leq 150/90$ mm Hg at the time of study entry and, if known to be hypertensive, have been on a stable dose of antihypertensive therapy for at least 1 week before Cycle 1 Day 1. Early detection and effective management of hypertension are important to minimize the need for lenvatinib dose interruptions and reductions.

Regular assessment of BP should be as detailed in the SoA (Section 1.3). Hypertension will be graded using NCI CTCAE v4.0, based on BP measurements only (and not on the number of antihypertensive medications).

If the participant’s first BP measurement of the current assessment is elevated (ie, systolic BP ≥ 140 mm Hg or diastolic BP ≥ 90 mm Hg), the BP measurement should be repeated at least 5 minutes later. One BP assessment is defined as the mean value of 2 measurements at least

5 minutes apart. If the BP assessment (ie, the mean of the 2 BP measurements obtained at least 5 minutes apart) is elevated (systolic BP ≥ 140 mm Hg or diastolic BP ≥ 90 mm Hg), a confirmatory assessment should be obtained at least 30 minutes later by performing 2 measurements (at least 5 minutes apart) to yield a mean value.

Antihypertensive agents should be started as soon as elevated BP (systolic BP ≥ 140 mm Hg or diastolic BP ≥ 90 mm Hg) is confirmed on 2 assessments at least 30 minutes apart. The choice of antihypertensive treatment should be individualized to the participant's clinical circumstances and follow standard medical practice. For previously normotensive participants, appropriate antihypertensive therapy should be started when systolic BP ≥ 140 mm Hg or diastolic BP ≥ 90 mm Hg is first observed on 2 assessments at least 30 minutes apart. For those participants already on antihypertensive medication, treatment modification may be necessary if hypertension persists.

Lenvatinib should be withheld in any instance where a participant is at imminent risk to develop a hypertensive crisis or has significant risk factors for severe complications of uncontrolled hypertension (eg, BP $\geq 160/100$ mm Hg, significant risk factors for cardiac disease, intracerebral hemorrhage, or other significant co-morbidities). Once the participant has been on the same antihypertensive medications for at least 48 hours and the BP is controlled, lenvatinib should be resumed as described below.

Participants who have had systolic BP ≥ 160 mm Hg or diastolic BP ≥ 100 mm Hg must have their BP monitored on Day 15 (or more frequently as clinically indicated) until systolic BP has been ≤ 150 mm Hg and diastolic BP has been ≤ 95 mm Hg for 2 consecutive treatment cycles. If a repeat event of systolic BP ≥ 160 mm Hg or diastolic BP ≥ 100 mm Hg occurs, the participant must resume the Day 15 evaluation until systolic BP has been ≤ 150 mm Hg and diastolic BP has been ≤ 95 mm Hg for 2 consecutive treatment cycles. A diary will be provided to the participant to capture the blood pressure evaluations between study visits.

The following guidelines should be followed for the management of systolic BP ≥ 160 mm Hg or diastolic BP ≥ 100 mm Hg confirmed on 2 BP assessments at least 30 minutes apart:

1. Continue study drug and institute antihypertensive therapy for participants not already receiving this.
2. For those participants already on antihypertensive medication, the dose of the current agent may be increased, if appropriate, or 1 or more agents of a different class of antihypertensive should be added. Study intervention can be continued without dose modification.
3. If systolic BP ≥ 160 mm Hg or diastolic BP ≥ 100 mm Hg persists despite maximal antihypertensive therapy, then lenvatinib administration should be interrupted and restarted at 1 dose level reduction only when systolic BP ≤ 150 mm Hg and diastolic BP ≤ 95 mm Hg and the participant has been on a stable dose of antihypertensive medication for at least 48 hours.

- If systolic BP ≥ 160 mm Hg or diastolic BP ≥ 100 mm Hg recurs on the first dose reduction despite optimal management of hypertension with antihypertensive medications (either by dose increase or the addition of a different class of antihypertensive), then lenvatinib administration should be interrupted and restarted at an additional dose reduction only when systolic BP ≤ 150 mm Hg and diastolic BP ≤ 95 mm Hg and the participant has been on a stable dose of antihypertensive medication for at least 48 hours.
- If systolic BP ≥ 160 mm Hg or diastolic BP ≥ 100 mm Hg recurs on the second dose reduction despite optimal management of hypertension with antihypertensive medications (either by dose increase or the addition of a different class of antihypertensive), then lenvatinib administration should be interrupted and restarted at a third dose reduction only when systolic BP ≤ 150 mm Hg and diastolic BP ≤ 95 mm Hg and the participant has been on a stable dose of antihypertensive medication for at least 48 hours.
- Additional dose reduction should be discussed with Sponsor.

The following guidelines should be followed for the management of Grade 4 hypertension (life-threatening consequences):

1. Institute appropriate medical management
2. Discontinue study drug

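### Section 6.6.2.1 gives opposite first actions for confirmed blood pressure of 160/100 mm Hg or above, and leaves the lenvatinib dose after a withhold unclear

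*Combined protocol and SAP*

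**What the plan says.** Section 6.6.2.1 (Management of Hypertension) handles severe hypertension in two parts.

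The first is a withhold paragraph: "Lenvatinib should be withheld in any instance where a participant is at imminent risk to develop a hypertensive crisis or has significant risk factors". The risk factors meant are those for severe complications. Its bracketed examples are BP of 160/100 mm Hg or above, cardiac risk factors, intracerebral hemorrhage and other co-morbidities. Once the same antihypertensives have been taken for at least 48 hours and "the BP is controlled, lenvatinib should be resumed as described below".

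The second is a numbered list for systolic BP of at least 160 or diastolic BP of at least 100 mm Hg, confirmed on two assessments at least 30 minutes apart:

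- Item 1: "Continue study drug and institute antihypertensive therapy for participants not already receiving this".
- Item 2, for participants already on antihypertensives, allows treatment to be intensified and adds: "Study intervention can be continued without dose modification".
- Item 3 applies if BP at that level "persists despite maximal antihypertensive therapy, then lenvatinib administration should be interrupted and restarted at 1 dose level reduction only when" BP is at or below 150/95 mm Hg on a stable antihypertensive dose for at least 48 hours.
- Two bullets deal with recurrence on a first or second reduced dose. The first reads: "then lenvatinib administration should be interrupted and restarted at an additional dose reduction only when" the same conditions are met. The second moves to a third reduction.

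Section 6.6.2 sends sites to these subsections "as appropriate, before consulting the dose modification table" (Table 6). Footnote b of Table 6 says: "Initiate optimal medical management for nausea, vomiting, hypertension, hypothyroidism, and/or diarrhea prior to any lenvatinib interruption or dose reduction".

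**The concern.** The two parts attach different first actions to overlapping BP limits. One site could stop lenvatinib in a participant with confirmed 160/100 mm Hg and another could continue it, and both could point to the protocol. The safety concern runs in both directions: dosing may continue where a withhold was intended, or stop where continuation was intended.

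The dose on resumption is a second, linked problem. Section 6.6.2 does not allow a reduced dose to be raised again unless the reduction was a mistake and the Sponsor approves. A site's reading of the forward pointer could therefore fix a participant's lenvatinib dose for the rest of treatment.

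**Working it through.** The plan states no figure to reproduce here. The check compares the texts, followed by simple arithmetic on the dose levels.

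**Step 1. Do the two parts cover the same participants?**

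| | Withhold paragraph | Numbered guidance |
|---|---|---|
| BP limit | 160/100 mm Hg or above, as an example of the trigger | Systolic at least 160 or diastolic at least 100 mm Hg |
| Confirmation | None stated | Two assessments at least 30 minutes apart |
| First action | Withhold | Continue (item 1), or may continue without dose change (item 2) |
| When interruption applies | At once | After persistence despite maximal therapy (item 3), or recurrence on a reduced dose |
| BP needed to resume | Controlled, no value given | At or below 150/95 mm Hg |
| Antihypertensive condition | At least 48 hours | At least 48 hours |
| Dose on resumption | Pointer to text below | One further level down each time |

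The limits overlap but are not identical. A participant at 165/85 mm Hg falls under the numbered guidance and does not plainly match the withhold example. A participant with confirmed BP of, say, 165/105 mm Hg falls under both.

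**Step 2. Does anything set precedence?** Section 6.6.2 puts the subsections ahead of Table 6 but gives no order within 6.6.2.1. Footnote b of Table 6 leans towards treating the hypertension before any interruption. The withhold paragraph's wording leans the other way. Sections 6.6.3, 7.1 and 8.3.2 do not settle it. Appendix 7 refers Canadian sites to the lenvatinib product monograph, which is not among the documents.

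**Step 3. Where does the resumption pointer lead?** Three restarts follow:

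1. Item 3: one level down, after persistence despite maximal therapy.
2. First bullet: a further level down, after recurrence on the first reduction.
3. Second bullet: a third level down, after recurrence on the second reduction.

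All 3 are at a reduced dose. None (0 of 3) is written for a participant withheld under the first paragraph before maximal therapy was tried.

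**Step 4. What is the difference worth?** Section 6.6.2 gives dose levels of 20, 14, 10 and 8 mg/day. The gap between resuming at the same dose and one level lower is (current − next) / current:

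- From 20: (20 − 14) / 20 = 30.0%
- From 14: (14 − 10) / 14 = 28.6%
- From 10: (10 − 8) / 10 = 20.0%

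**Step 5. How many participants?** This cannot be computed, because the documents do not give the share reaching 160/100 mm Hg. Section 2.2.1.6 reports treatment-related hypertension of any grade in 48% of 21 melanoma participants on the same regimen. That shows hypertension is common with this combination, but not how often it reaches these limits.

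**The case against.** The best reply is that the withhold paragraph is a risk test and that BP appears only in its list of examples. If BP of 160/100 mm Hg always triggered a withhold, items 1 and 2 would have little left to do. Both parts can be given effect by treating the numbered list as the default and the withhold paragraph as an exception for high-risk participants. On this view the paragraph's broad wording acts as an override.

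That reading is coherent and may be what was intended, but the text does not state it. BP at that level is itself an example of the trigger, so it cannot separate the two groups, and items 1 to 3 make no exception for high-risk participants.

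On resumption, it can be said that every restart below is at a reduced dose, that each repeats the 48-hour condition, and that Table 6 pairs interruption with a one-level reduction for intolerable Grade 2 or Grade 3 toxicity. The pointer might therefore already mean a reduced dose. This has some force, and neither 6.6.2.1 nor Table 6 describes a restart at the same dose. Even so, each restart in 6.6.2.1 depends on persistence or recurrence, so applying it to a first-paragraph withhold is an inference.

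Two further points stand. The percentages in the working matter only if sites do differ in the dose at which they resume. And the response rate, its exact confidence interval and the analysis population are untouched.

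**Conclusion.** The concern holds. Section 6.6.2.1 gives conflicting first actions for a participant with confirmed BP at or above both 160 systolic and 100 diastolic, with no stated precedence. It also gives no clear lenvatinib dose for resuming after a first-paragraph withhold.

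This is an internal inconsistency in safety management. It bears on participant safety and on consistency of lenvatinib exposure across sites. The difference per affected participant is 20.0% to 30.0% of the daily dose, assuming the alternatives are the same dose or one level lower from 20, 14 or 10 mg/day. The number affected is unknown. The conclusion rests on the protocol text alone and takes no view on which clinical rule or dose is right.

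**What to change.** The sponsor should reconcile the two parts of Section 6.6.2.1 by stating:

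- which participants fall under the withhold paragraph and which under the numbered guidance;
- which part governs when both apply;
- what BP counts as controlled for resumption after a first-paragraph withhold, and at what dose lenvatinib then resumes.

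Footnote b of Table 6 should be checked against the result. The clinical choice is the sponsor's. The cost is a protocol wording change and a clarification letter to sites, with no change to the sample size or any planned analysis.

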6.6.2.2 Management of Proteinuria

Regular assessment of proteinuria should be conducted as detailed in the SoA (Section 1.3). Guidelines for assessment and management of proteinuria are as follows:

Detection and Confirmation

1. Perform urine dipstick testing per the SoA (Section 1.3).
2. A 24-hour urine collection initiated as soon as possible and at least within 72 hours (or an immediate spot urine protein-to-creatinine ratio [UPCR] test) is required in the following situations:
 - The first (initial) occurrence of $\geq 2+$ proteinuria on urine dipstick while on study drug
 - A subsequent increase in severity of urine dipstick proteinuria occurring on the same lenvatinib dose level
 - When there has been a lenvatinib dose reduction, and at the new dose level the urine protein dipstick result is $\geq 2+$.

3. A 24-hour urine collection (initiated as soon as possible and at least within 72 hours) to verify the grade of proteinuria is required when UPCR is ≥ 2.4 .

Grading of Proteinuria

- Grading according to NCI CTCAE v4.0 will be based on the 24-hour urinary protein result if one has been obtained. Management of lenvatinib administration will be based on the grade of proteinuria according to [Table 6](#).
- In the event of nephrotic syndrome, lenvatinib must be discontinued.

Monitoring

- Urine dipstick testing for participants with proteinuria $\geq 2+$ should be performed on Day 15 (or more frequently as clinically indicated) until the results have been 1+ or negative for 2 consecutive treatment cycles.
- Proteinuria monitoring can be performed at the local laboratory or investigator site but must be managed by the site physician.

6.6.2.3 Management of Diarrhea

An antidiarrheal agent should be recommended to the participant at the start of study intervention, and participants should be instructed and educated to initiate antidiarrheal treatment at the first onset of soft bowel movements. The choice of antidiarrheal agent should be individualized to the participant's clinical circumstances and follow standard medical practice. If signs/symptoms of diarrhea persist despite optimal medical management, instructions contained in [Table 6](#) should be followed.

6.6.2.4 Management of Hepatotoxicity

Liver function tests (ALT, AST, and bilirubin levels) should be conducted as detailed in the SoA (Section 1.3) and as clinically indicated. If signs/symptoms indicating liver injury occur, instructions contained in [Table 6](#) should be followed. Appropriate supportive care should be provided together with close monitoring. If hepatic failure occurs, the study drug must be discontinued.

6.6.2.5 Management of Thromboembolic Events

Participants should be advised to pay attention to symptoms suggestive of venous thromboembolic events, which include acute onset of shortness of breath, dyspnea, chest pain, cough, hemoptysis, tachypnea, tachycardia, cyanosis, deep vein thrombosis signs including lower-extremity swelling, and warmth to touch or tenderness. In case any of these symptoms appear, participants should be instructed to report such symptoms promptly to the treating physician. If a thromboembolic event is confirmed, instructions contained in [Table 6](#) should be followed. Appropriate supportive care should be provided together with close monitoring. Lenvatinib must be discontinued for a Grade 3 thromboembolic event that requires urgent intervention. If a participant experiences a Grade 3 or a life-threatening

(Grade 4) thromboembolic reaction, including pulmonary embolism, lenvatinib/placebo must be discontinued.

Arterial thromboembolic events (eg, new onset, worsening, or unstable angina, myocardial infarction, transient ischemic attack, and cerebrovascular accident) of any grade require study intervention discontinuation.

6.6.2.6 Management of Posterior Reversible Encephalopathy Syndrome/Reversible Encephalopathy Syndrome/Reversible Posterior Leukoencephalopathy Syndrome

Posterior Reversible Encephalopathy Syndrome/Reversible Encephalopathy Syndrome/Reversible Posterior Leukoencephalopathy Syndrome (PRES/RPLS) is a neurological disorder that can present with headache, seizure, lethargy, confusion, altered mental function, blindness, and other visual or neurological disturbances. Mild to severe hypertension may be present. MRI is necessary to confirm the diagnosis of PRES/RPLS. Appropriate measures should be taken to control BP. In participants with signs or symptoms of PRES/RPLS, instructions in [Table 6](#) should be followed.

6.6.2.7 Management of Hypocalcemia

Serum calcium should be monitored per the SoA (Section 1.3). Corrected serum calcium should be used to assess the grade of hypocalcemia per CTCAE v4.0, using the following formula:

$$\text{Corrected calcium} = ([4 - \text{serum albumin in g/dL}] \times 0.8 + \text{serum calcium}).$$

The formula is not applicable when serum albumin concentration is normal (>4 g/dL); in such situations, the total (uncorrected) serum calcium should be used instead.

Hypocalcemia should be treated per institutional guidelines (eg, using appropriate calcium, magnesium, and vitamin D supplementation) until resolution.

6.6.2.8 Management of Hemorrhage

Instructions in [Table 6](#) should be followed for the management of hemorrhage. Either resume at a reduced dose or discontinue lenvatinib depending on the severity and persistence of hemorrhage.

6.6.2.9 Management of Gastrointestinal Perforation or Fistula Formation

Lenvatinib should be discontinued in any participants who develop gastrointestinal perforation of any grade or \geq Grade 4 fistula.

6.6.2.10 Management of Osteonecrosis

Perform an oral examination prior to treatment with lenvatinib and periodically during lenvatinib treatment. Advise participants regarding good oral hygiene practices. Avoid

invasive dental procedures, if possible, while on lenvatinib treatment, particularly in participants at higher risk. For participants requiring invasive dental procedures, discontinuation of bisphosphonate treatment may reduce the risk of ONJ. Withhold lenvatinib if ONJ develops and restart based on clinical judgment of adequate resolution (see Section 6.6.4).

6.6.3 Dose Modifications for Overlapping Toxicities

Based on the known toxicity profiles of pembrolizumab and lenvatinib, certain treatment-related AEs are uniquely associated with one drug versus the other. For example, hypertension, arterial thrombotic events, proteinuria, and hemorrhagic events are known risks for lenvatinib treatment, while immune-related AEs are risks for pembrolizumab treatment. However, certain AEs, such as diarrhea, hypothyroidism, and liver enzyme elevation, may be initially considered attributable to either study drug. Therefore, evaluation of attribution is important for determining the study drug most likely related to the AE, or an alternative etiology, and subsequently proper clinical management. The following aspects should be considered:

1. Timing of AE onset

Since lenvatinib is dosed daily and continuously due to a relatively short half-life (~28 hours), and pembrolizumab is dosed Q3W due to a long half-life, lenvatinib can be interrupted to assess whether an AE improves/resolves with dechallenge (ie, interruption of treatment) based on the following 2 scenarios:

- If an AE is identified during a treatment cycle (ie, between 2 pembrolizumab doses), only lenvatinib dose interruption is needed.
- If an AE is identified at the beginning of a treatment cycle, lenvatinib can be interrupted and dosing of pembrolizumab should be held.

If the participant recovers from an AE in response to lenvatinib interruption (ie, positive dechallenge), the event is more likely to be related to lenvatinib. Otherwise, after excluding other alternative explanations, an immune-related AE should be considered.

2. Severity of AE

If an AE is suspected to be treatment related and is severe/life threatening at the time of onset or is rapidly worsened, action including interrupting both drugs and initiating treatment with a corticosteroid (with exception of hypothyroidism, T1DM) and other supportive care should be taken promptly.

3. Participants receiving the combination therapy (pembrolizumab + lenvatinib) must discontinue study intervention if any of the following occur:
 - ALT or AST $>5 \times$ ULN for more than 2 weeks
Pembrolizumab will have already been permanently discontinued per Table 4, but lenvatinib may be administered at a reduced dose by the time this criterion is met and must be permanently discontinued immediately.
 - ALT or AST $>3 \times$ ULN and (TBL $>2 \times$ ULN or INR >1.5)
Although Table 4 advises pembrolizumab to be withheld (interrupted), and Table 6 advises lenvatinib to have no dose modification or a reduction, if this criterion is met, both drugs must be permanently discontinued immediately.

